8.3.4 Intervention

Any intervention implemented to treat the adverse event must be documented for all adverse events.

8.4 Safety Reporting

8.4.1 **Reporting to IRB**

8.4.1.1 Unanticipated Problems

All incidents or events that meet criteria for unanticipated problems (UAPs) as defined in Section 8.1.1 Unanticipated Problems require the creation and completion of an unanticipated problem report form (OHR-20).

UAPs that pose risk to participants or others, and that are not AEs, will be submitted to the IRB on an OHR-20 form via the eazUP system within 10 working days of the investigator becoming aware of the event.

UAPs that do not pose risk to participants or others will be submitted to the IRB at the next continuing review.

8.4.1.2 Adverse Events

Grade 1 AEs will be reported to the IRB at continuing review.

Grade 2 AEs will be reported to the IRB at the time of continuing review.

8.4.1.3 Serious Adverse Events

SAEs will be reported to the IRB on OHR-10 forms via the electronic reporting system (eSAEy) according to the required time frames described below.

Grade 3-4 AEs that are unexpected and deemed to be at least possibly related to the study will be reported to the IRB within 2 working days of knowledge of the event.

Grade 3-4 AEs that are deemed unrelated to the study will be reported to the IRB within 5 working days.

Grade 5 AEs will be reported to the IRB within one working day of knowledge of the event.

All SAEs will be submitted to the IRB at continuing review, including those that were reported previously.

8.4.2 **Reporting to SKCC DSMC**

All AEs and SAEs, safety and toxicity data, and any corrective actions will be submitted to the DSMC per the frequency described in the SKCC DSMP. The report to the SKCC DSMC will also include any unanticipated problems that in the opinion of the PI should be reported to the DSMC.

All non-hematologic adverse events will be reported to the DSMC.

The only hematologic events which will be considered a DLT/AE/SAE for this study are (i) marrow aplasia (defined as <10% cellularity with <10% blasts for \geq 6 weeks not attributable to disease) (ii) grade 4 neutropenia persisting \geq 6 weeks from the start of a cycle that is not attributable to the underlying disease and this will be reported.

All hematologic grade 5 SAEs will be reported to the DSMC regardless of causality.

For expedited reporting requirements, see table below:

DSMC AE/SAE Reporting Requirements

	Grade 1	Gra	de 2		Gı	ade 3		Grades 4 and 5
	Unexpected and Expected	Unexpected	Expected	Unex With Hospitalization	Unexpected Expected With Iospitalization Without Hospitalization With Hospitalization		Without Hospitalization	Unexpected and Expected
Unrelated Unlikely	Reviewed at Quarterly DSMC Meeting and	Reviewed at Quarterly DSMC Meeting and	Reviewed at Quarterly DSMC Meeting and	5 Working Days	Reviewed at Quarterly DSMC Meeting and IRB Annual	5 Working Days	Reviewed at Quarterly DSMC Meeting and IRB Annual	Phase I - 48 Hours (Death: 24 Hours)
	IRB IRB IRB Annual Annual Review Review Review			Review		Review	Phase II - 5 working days	
Possib le Prob ab ly	Reviewed at Quarterly DSMC Meeting	Reviewed at Quarterly DSMC Meeting	Reviewed at Quarterly DSMC Meeting	48 Hours (Death: 24	Phase I - 48 Hours	48 Hours (Death: 24	Reviewed at Quarterly DSMC	Phase I and Phase II - 48 Hours
Definite	and and and Hours) IRB IRB IRB Annual Annual Annual Review Review		Phase II - 5 working days	Hours)	Review	(Death: 24 Hours)		

8.4.3 **Reporting to Funding Sponsor**

SAEs, as well as all other safety information at the end of the study or as requested by the funding sponsor, will be reported to Pfizer within 24 hours of occurrence by faxing the Pfizer SAE Event Form to the Pfizer US Clinical Trial Department at [name] (Appendix E).

Serious adverse events and all other safety information as defined below will be collected from day -7 of the lead-in period with palbociclib until 28 days after discontinuation. Safety Information is defined as any information from any source containing information such as:

- Adverse event or suspicion thereof
- Lack of efficacy
- Overdose/incorrect dosage (accidental or intentional)
- Abuse/misuse (e.g., patients sharing medication) even without resulting adverse reaction
- Accidental exposure (e.g., child takes parents medication)
- Medication error
- Withdrawal reactions
- Disease progression/exacerbation of existing disease
- Drug-drug/Drug-food interaction
- Reports of unexpected benefit
- Exposure to drug during pregnancy, where the embryo or fetus may have been exposed to medicinal products (either through maternal exposure or transmission of a medicinal product via semen following paternal exposure).
- Exposure to drug during lactation (including uneventful)
- Suspected counterfeit product
- Suspected transfer of infectious disease/agent by the medicinal product concerned.
- Product complaint report (any deficiencies related to the identity, quality, labeling, durability, reliability, efficacy, performance of a medicinal product, suspected counterfeit product)
- Pediatric use (if not an approved use)
- Occupational exposure
- Off-label use (if not part of the study design)

8.4.4 **Reporting to FDA**

For studies conducted under an Investigator IND in the US, any event that is both serious and unexpected must be reported to the Food and Drug Administration (FDA) as soon as possible and no later than 7 days (for a death or life-threatening event) or 15 days (for all other SAEs) after the investigator's or institution's initial receipt of the information. Pfizer Inc. will be provided with a simultaneous copy of all adverse events filed with the FDA.

SAEs will be reported on MedWatch Form 3500A, which can be accessed at: http://www.accessdata.fda.gov/scripts/medwatch/.

MedWatch SAE forms will be sent to the FDA at:

MEDWATCH [name] [name] [name] Fax: [name] ([name]) http://www.accessdata.fda.gov/scripts/medwatch/

9 Study Oversight

In addition to the PI's responsibility for oversight, study oversight will be under the direction of the SKCC's Data and Safety Monitoring Committee (DSMC). The SKCC DSMC operates in compliance with a Data and Safety Monitoring Plan (DSMP) that is approved by the NCI.

10 Clinical Site Monitoring and Auditing

Clinical site monitoring and auditing is conducted to ensure that the rights of human participants are protected, that the study is implemented in accordance with the protocol and/or other operating procedures, and that the quality and integrity of study data and data collection methods are maintained. Monitoring and auditing for this study will be performed in accordance with the SKCC's Data and Safety Monitoring Plan (DSMP) developed by the SKCC Data and Safety Monitoring procedures, the level of clinical site monitoring activities (e.g., the percentage of participant data to be reviewed), and the distribution of monitoring reports. Some monitoring activities may be performed remotely, while others will take place at the study site(s). Appropriate staff will conduct monitoring activities and provide reports of the findings and associated action items in accordance with the details described in the SKCC DSMP.

11 Statistical Considerations

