1.2 Rationale for the Proposed Study

This study will evaluate the use of palbociclib in conjunction with dexamethasone for the treatment of relapsed or refractory ALL. We will begin giving palbociclib at a dose of 100mg PO daily with escalation in increments of 25mg to a maximum dose of 150mg. Initial Phase I testing of palbociclib in patients with advanced solid tumors revealed a maximum tolerated dose (MTD) of 125mg daily. The primary dose limiting toxicity was bone marrow suppression, an important consideration when treating sold tumors, but an expected, and possible surrogate marker for efficacy, in the treatment of leukemia. Dexamethasone may decrease serum drug levels of palbociclib, so we will begin with a palbociclib dose of 100mg and escalate from there. Dosing regimens in ALL vary; in this study, we propose giving dexamethasone at a starting dose of 20mg daily in conjunction with palbociclib, and then decreasing the dose by 4mg weekly over 4 weeks to minimize side effects.

If the combination of palbociclib and dexamethasone is found to be safe and well-tolerated, we would hope to move forward with a larger, Phase II study.

1.3 **Correlative Studies**

The following correlative studies will be performed in the [name] Laboratory:

- 1. RB phosphorylation (CDK4/6 phosphorylation sites) by Western blot as the primary read-out of palbociclib activity.
- 2. FOXM1 expression by Western blot as the secondary read-out of palbociclib activity (since FOXM1 is a CDK4/6 target)

- 3. RNA isolated from CD19+ cells will be used for gene expression profiles (microarray or RNA-Seq) to measure p21 expression as an indicator of cell cycle activity
- RNA isolated from CD19+ cells will be used for gene expression profiles (microarray or RNA-Seq) to measure S-Phase, Annexin V/Caspase 3 activation as indicators of proliferation and apoptosis
- RNA isolated from CD19+ cells will be used for gene expression profiles (microarray or RNA-Seq) to measure Expression of Myb and Bcl-2 as a read-out of dexamethasone sensitivity

These analyses will be performed on pre-treatment samples (peripheral blood and/or bone marrow) as well as on day +1 (after 1 week of palbociclib alone) and day +8 (after 1 week of combined therapy) of treatment (peripheral blood).

1.4 **Potential Risks and Benefits**

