8.1.2 Adverse Events

An adverse event is any untoward or unfavorable medical occurrence in a human participant, including any abnormal sign (for example, abnormal physical exam or laboratory finding), symptom, or disease, temporally associated with the participant's participation in the research, whether or not considered related to the participant's participation in the research.

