** Optimal therapy for vomiting and diarrhea should be based on institutional guidelines with consideration of the prohibited medications listed in these protocol guidelines.

The design is constructed to reduce the chance of escalating the dose when the probability of DLT is high, and increase the chance of escalating the dose when the probability of DLT is low. The maximum tolerated dose (MTD) is defined as the highest dose level where a DLT occurs in at most one out of six patients treated. The escalation scheme is as follows:

(1) If none of the initial three patients in a cohort experiences a DLT, then a new cohort of three patients will be treated at the next higher dose level.

(2) If one of the three patients in a cohort experiences a DLT, then up to three additional patients will be treated at the same dose. Escalation will continue if only one of six patients experiences DLT.

(3) If two or more patients in a cohort experience DLT, then the MTD will have been exceeded, and no further dose escalation will occur. The previous dose level will be considered the MTD.

(4) If only three patients were treated at a dose level under consideration as the MTD, then up to three additional patients will be accrued. If no more than one of the six patients at that dose level experience a DLT, then that dose level will be confirmed as the MTD. If two or more patients in that cohort experience DLT, then the previous dose level will be studied in the same fashion.

The MTD is defined as the highest dose studied for which the observed incidence of DLT is less than 33%. Frequencies of toxicities will be tabulated according to the NCI Common Toxicity Criteria. Patients will be continued to be followed for one year for evidence of late toxicity.

Table 1.1 below gives the probabilities of dose escalation based on true DLT risk in the 3+3 design.

True DLT rate										
		10%	20%	30%	40%	50%	60%	70%	80%	90%
Probability c escalation	of	0.91	0.71	0.49	0.31	0.17	0.08	0.03	0.01	0.001

All patients treated with at least one dose will be included in the safety analysis.

Response criteria for the study are defined as follows:

Response Criteria Complete Remission (CR) No lymphoblasts in the bone marrow Absolute neutrophil count ≥0.75 x10⁹/L Platelet count ≥75 x 10⁹ /L

Complete Remission with Incomplete Hematologic Recovery (CRi)

<5% lymphoblasts in the bone marrow

Partial Remission (PR)

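### Read literally, section 8.4.2 takes most cytopenias out of the AE/SAE record, contradicts 8.1.2, 8.1.3 and 1.4.1, and leaves their place in the safety tables undefined

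*Combined protocol and SAP*

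**What the plan says.** Section 8.4.2 (Reporting to SKCC DSMC) opens broadly: "All AEs and SAEs, safety and toxicity data, and any corrective actions will be submitted to the DSMC". It then says that all non-hematologic AEs go to the committee, and narrows the hematologic side: "The only hematologic events which will be considered a DLT/AE/SAE for this study are (i) marrow aplasia", with a duration of six weeks or more and not due to disease. The second event on the list is Grade 4 neutropenia lasting at least six weeks "from the start of a cycle that is not attributable to the underlying disease and this will be reported". The next sentence reads: "All hematologic grade 5 SAEs will be reported to the DSMC regardless of causality".

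The general definitions are wider. In 8.1.2 an adverse event is any unfavorable occurrence, "including any abnormal sign (for example, abnormal physical exam or laboratory finding), symptom, or disease", whether or not related to participation. Section 8.1.3 makes an event serious if, among other criteria, it is life-threatening or leads to hospitalization, and it has no hematologic exception. Section 1.4.1 names myelosuppression first among the anticipated treatment-related adverse events.

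On the drug, 1.2 reports of the first solid-tumor testing: "The primary dose limiting toxicity was bone marrow suppression". It adds that this effect is expected in leukemia and may even signal efficacy. Safety and tolerability is a primary objective (2.1.1). The only planned safety summary is in 11.2: "Frequencies of toxicities will be tabulated according to the NCI Common Toxicity Criteria", with every patient who took at least one dose in the safety analysis.

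**The concern.** A narrow hematologic DLT definition is a defensible choice in leukemia, where marrow suppression is expected. The 8.4.2 sentence goes further. It puts AE and SAE under the same restriction as DLT, and its scope is the study, not one committee's mailbox. Staff who follow it would not enter most cytopenias as AEs. Staff who follow 8.1.2 would enter all of them. The same blood count could be handled either way.

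At stake is how marrow toxicity is described at each dose level, which a sponsor planning Phase II will want to see. Reporting to the IRB (8.4.1) and to the funder (8.4.3) also turns largely on whether an event is an AE or SAE. Reporting to the FDA (8.4.4) covers events that are both serious and unexpected, so there the question bites only for a cytopenia whose nature, severity or frequency goes beyond the known risk.

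**Working it through.** The plan states no figure on this point, so the check is mainly a comparison of text.

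**Step 1. Classify each kind of event under both sets of rules.**

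| Event | 8.4.2 read literally | 8.1.2 and 8.1.3 |
|---|---|---|
| Non-fatal anemia or thrombocytopenia, any grade or duration (unless part of qualifying aplasia) | Not an AE or SAE | AE; SAE if a seriousness criterion is met |
| Non-fatal neutropenia, Grade 1-3, any duration | Not an AE or SAE | Same as above |
| Non-fatal Grade 4 neutropenia under 6 weeks | Not an AE or SAE | Same as above |
| Non-fatal Grade 4 neutropenia of 6 weeks or more, due to disease | Not an AE or SAE | Same as above; relatedness is irrelevant |
| Grade 4 neutropenia or marrow aplasia of 6 weeks or more, not due to disease | DLT/AE/SAE | AE; SAE if a seriousness criterion is met |
| Fatal hematologic event | Not on the list as such, yet reportable as an SAE whatever the cause | SAE |

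The first four rows conflict directly. The last row conflicts inside 8.4.2: both listed events exclude disease as the cause, so a rule for fatal hematologic SAEs of any cause presupposes SAEs that the list does not allow.

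**Step 2. Does the DLT endpoint cover the gap?** Inputs: a DLT period of 35 days, that is 7 lead-in days plus 28 days of Cycle 1 (6.2.1), and a six-week criterion, 6 × 7 = 42 days.
- Counted from day -7: 42 − 35 = 7 days after the period closes.
- Counted from Cycle 1 day 1, as the reference to the start of a cycle suggests: 7 + 42 = 49 elapsed days, and 49 − 35 = 14 days after it closes.

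Aplasia that begins on treatment cannot complete six weeks inside the period either. So within the formal DLT window neither listed event can be completed, and a comparison of marrow toxicity across doses rests heavily on the AE or toxicity tables. This is noted only to show why those tables matter; what should count as a DLT is a separate clinical question.

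**Step 3. Is there another route into the tables?** Partly. Appendix A schedules a CBC at baseline, on induction Days 1, 4, 8, 12, 14, 21 and 28, weekly in the first maintenance cycle and every other week in cycles 2-6. Section 5.4 grades neutropenia, anemia and thrombocytopenia as hematologic toxicity. The tabulation in 11.2 speaks of toxicities and does not refer to 8.4.2. But no passage says that it includes cytopenias which 8.4.2 does not count as AEs, and no worst-grade or shift table is planned.

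**Step 4. Can the number of affected patients be given?** It would be n × r, where r is the share of patients with a cytopenia that falls off the list. The documents give no r, and for the maximum n they give both 18 (3.1 and 11.3) and 24 (11.3). With r assumed anywhere from 0.30 to 0.90, the count runs from 0.30 × 18 = 5.4 to 0.90 × 18 = 16.2, or from 0.30 × 24 = 7.2 to 0.90 × 24 = 21.6. A range that wide is not an estimate, and it applies only on the literal reading.

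**The case against.** The best defense is structural. Definitions sit in 8.1, recording in 8.3 and reporting in 8.4. Section 8.3 governs what is documented and sends the reader to 8.4 for reporting only. The disputed sentence stands under the DSMC heading, follows a sentence on what goes to the DSMC, and ends by saying that the events will be reported. The grade 5 sentence makes sense only if other hematologic SAEs exist. On this view 8.4.2 is a reporting carve-out and nothing is lost from the record.

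That reading is plausible and may be what was meant. It does not remove the problem, because the sentence says what an event is considered to be for the study, and no other text confines it to the DSMC.

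The defense does defeat several stronger inferences that a reader might draw:
- *That the trial would report safety without its drug's main toxicity, or would understate it at every dose.* This does not follow. Prolonged aplasia, prolonged Grade 4 neutropenia and fatal events remain; the counts are collected; safety and toxicity data go to the DSMC; and 11.2 is not tied to 8.4.2.
- *That palbociclib is held or reduced for every Grade 3-4 cytopenia that goes unrecorded.* Section 5.4 does not say that. Its grade-based rules apply to patients who stay on maintenance after the first cycle. They act on anemia only at Grade 4, on Grade 3 thrombocytopenia only on Day 1 of a cycle, and on Grade 3 neutropenia only on Day 1 or with fever or infection.
- *That a given number of patients would be tabulated as zero.* This needs an assumed rate and the disputed reading together.
- *That the MTD would be wrong.* The MTD in 11.2 depends on DLTs, and the escalation meeting in 6.2.1 reviews safety information without limiting it to the events in 8.4.2.

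**Conclusion.** The concern holds as a contradiction in a stated rule. Section 8.4.2, as worded, cannot stand beside 8.1.2, 8.1.3, 1.4.1 and its own next sentence, and the plan does not say which governs. The consequence is uncertainty, not a demonstrated loss of data: whether cytopenias enter the safety tables and the AE/SAE reporting depends on which reading staff adopt. Its size in patients cannot be stated. It deserves correction before the safety data are tabulated, because safety is a primary objective and marrow suppression is the toxicity that the protocol itself puts first. The conclusion rests on the wording alone and on no assumed event rate.

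**What to change.** 1. In 8.4.2, limit the sentence to which hematologic events count as DLTs. If the sponsor wants fewer urgent notices for expected cytopenias, say separately that these are exempt from expedited DSMC reporting.
2. State that 8.1.2 and 8.1.3 govern the recording and the seriousness of hematologic events, so that the grade 5 sentence and 1.4.1 agree with the rest.
3. Add to 11.2 a table by dose level of worst CTCAE grade and shift from baseline for neutrophils, hemoglobin and platelets, in all patients who took at least one dose. Take it from the CBCs in Appendix A, graded under the version that 8.3.3 names for adverse events. Show baseline grade, since the disease itself causes cytopenias.

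The first two changes resolve the contradiction. The third makes the marrow safety summary independent of how AEs were entered. The cost is a few sentences, somewhat more AE entry and one extra table, with no new sampling. The DLT criteria and the dosing rules stay as they are.

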11.1 Study Hypotheses

No formal hypotheses will be tested in this Phase I study.

11.2 Analysis Plans

This aim will consist of a Phase I trial of palbociclib to determine the maximum tolerated dose (MTD) of palbociclib when given in combination with dexamethasone. A standard 3+3 dose escalation design will be employed: three dose levels of palbociclib will be explored (100mg, 125mg, 150mg). Patients will be treated in cohorts of size three to six and the dosage will be escalated if the clinical toxicity is acceptable.

Patients who experience a DLT during the evaluation period as defined in section 6.2.1 will stop the study drugs and come off of the trial.

Patients who complete the first cycle of maintenance but require treatment to be held up to 4 weeks to achieve count recovery, will have palbociclib resumed with a level -1 dose reduction. A dose-limiting toxicity (DLT) is defined in the table below:

Toxicity	DLT Criteria*								
Hematology	 Marrow aplasia (defined as <10% cellularity with <10% blasts for ≥ 6 weeks not attributable to disease) 								
	• Grade 4 neutropenia persisting ≥6 weeks from the start of a cycle that								
	is not attributable to the underlying disease								
Cardiac	Any ≥ Grade 3 toxicity								
Gastro-intestinal	Any ≥ Grade 3 toxicity except:								
	 Grade 3 nausea, vomiting**, or diarrhea** not requiring total parenteral nutrition (TPN) or tube-feeding 								
Hepato-biliary	An increase in AST or ALT >3 x ULN and concurrent increase in total								
	bilirubin >2 x ULN (Hy's Law)								
	Any \geq Grade 3 toxicity except:								
	Any Grade 3 or 4 liver abnormalities (AST, ALT, or alkaline								
	phosphatase) that resolve to < grade 2 within 72 hours								
	 Grade 3 hyperbilirubinemia that resolves to < grade 2 within 72 hours One de 2 in dimensional that resolves to < grade 2 within 72 hours 								
	 Grade 3 indirect hyperbilirubinemia that resolves to < grade 2 within 72 hours 								
	nours								
Renal	Any ≥ Grade 3 toxicity								
Non-	≥ Grade 3, except as noted elsewhere in the table								
Hematologic									
Exceptions to	Grade 3 alopecia								
DLT criteria	 Grade 3 fatigue of < 5 days' duration 								
	 Grade 3 electrolyte abnormalities that last <72 hours 								
	 Infection, unless the investigator determines that the infection resulted 								
	from the degree or duration of myelosuppression in the absence of persistent leukemia								

* CTCAE version 5.0 should be used for grading.

** Optimal therapy for vomiting and diarrhea should be based on institutional guidelines with consideration of the prohibited medications listed in these protocol guidelines.

The design is constructed to reduce the chance of escalating the dose when the probability of DLT is high, and increase the chance of escalating the dose when the probability of DLT is low. The maximum tolerated dose (MTD) is defined as the highest dose level where a DLT occurs in at most one out of six patients treated. The escalation scheme is as follows:

(1) If none of the initial three patients in a cohort experiences a DLT, then a new cohort of three patients will be treated at the next higher dose level.

(2) If one of the three patients in a cohort experiences a DLT, then up to three additional patients will be treated at the same dose. Escalation will continue if only one of six patients experiences DLT.

(3) If two or more patients in a cohort experience DLT, then the MTD will have been exceeded, and no further dose escalation will occur. The previous dose level will be considered the MTD.

(4) If only three patients were treated at a dose level under consideration as the MTD, then up to three additional patients will be accrued. If no more than one of the six patients at that dose level experience a DLT, then that dose level will be confirmed as the MTD. If two or more patients in that cohort experience DLT, then the previous dose level will be studied in the same fashion.

The MTD is defined as the highest dose studied for which the observed incidence of DLT is less than 33%. Frequencies of toxicities will be tabulated according to the NCI Common Toxicity Criteria. Patients will be continued to be followed for one year for evidence of late toxicity.

Table 1.1 below gives the probabilities of dose escalation based on true DLT risk in the 3+3 design.

True DLT rate										
		10%	20%	30%	40%	50%	60%	70%	80%	90%
Probability c escalation	of	0.91	0.71	0.49	0.31	0.17	0.08	0.03	0.01	0.001

All patients treated with at least one dose will be included in the safety analysis.

Response criteria for the study are defined as follows:

Response Criteria Complete Remission (CR) No lymphoblasts in the bone marrow Absolute neutrophil count ≥0.75 x10⁹/L Platelet count ≥75 x 10⁹ /L

Complete Remission with Incomplete Hematologic Recovery (CRi)

<5% lymphoblasts in the bone marrow

Partial Remission (PR)

All criteria for CR are satisfied except there are between 5% and 25% lymphoblasts in the bone marrow

Stable Disease (SD)

Failure to achieve at least a PR, but with no evidence of progression as defined as an increase of peripheral blood or bone marrow blasts of more than 10% from nadir during study.

Progressive Disease (PD)

For patients with < 5% blasts at baseline, there must be an increase to \ge 10% blasts. For patients with 5% to 10% blasts at baseline, there must be a \ge 50% increase to > 10% blasts.

For patients with 10% to 20% blasts at baseline, there must be a \ge 50% increase to \ge 20% blasts.

Response rate defined as the proportion of patients who achieve a CR, CRi, PR, or SD response will be estimated along with a 95% confidence interval.

